6.2.13.2 Bruising

The Bruising assessment will be performed by the investigator at each in clinic visit starting at Month 1.

Bruising assessments (visual rating) will be performed using the following ratings:

Symptom	Rating (circle)
M207 application sites have bruising spots?	0 (clear) = None 1 (mild) = $\leq 25\%$ Present in the upper arm region of all M207 applications 2 (moderate) = ≥ 26 to $\leq 50\%$ Present in the upper arm region of all M207 applications 3 (severe) = $> 50\%$ Present in the upper arm region of all M207 applications

6.2.13.3 Other Skin Assessments – Erythema and Edema

Erythema and Edema will be assessed by the investigator at each in clinic visit starting at Month 1.

The following ratings will be used to describe the amount of erythema and edema indicative of irritation:

Symptom	Rating (circle)
Skin Erythema	0 (clear) = None 1 (mild) = $\leq 25\%$ Present in the upper arm region of all M207 applications 2 (moderate) = ≥ 26 to $\leq 50\%$ Present in the upper arm region of all M207 applications 3 (severe) = $> 50\%$ Present in the upper arm region of all M207 applications

Symptom	Rating (circle)
Skin Edema	0 (clear) = None 1 (mild) = $\leq 25\%$ Present in the upper arm region of all M207 applications 2 (moderate) = ≥ 26 to $\leq 50\%$ Present in the upper arm region of all M207 applications 3 (severe) = $> 50\%$ Present in the upper arm region of all M207 applications

Adverse Events of Special Interest: Any site reactions requiring further evaluation or care (e.g., by a dermatologist), as well as those resulting in scarring are considered adverse events of special interest. If these reactions are detected, the de-identified photograph of the patch application site and contralateral arm (containing the date of photograph, visit number and subject number) must be transmitted to the sponsor within 24 hours of the clinic visit for further dermatological evaluation.

7 STATISTICS

A complete description of the statistical analyses to be performed will be provided in a statistical analysis plan (SAP), which will be finalized prior to database lock.

7.1 Analysis Variables

7.1.1 Safety Endpoints

- Changes from baseline in physical examination findings at Months 6 and 12
- Changes from baseline in vital signs at Months 1, 2, 3, 6, 9, 12, and at the 2-week post-study visit
- Changes from baseline in clinical laboratory parameters at Month 12
- Changes from baseline and/or shifts in 12-lead ECG parameters at Months 6 and 12
- Frequency of concomitant medications
- Incidence of treatment-emergent systemic and skin AEs (TEAEs)
- Frequencies of type of redness, severity of swelling, amount of bruising, and amount of bleeding (30 minutes only) at the application site as reported by the subject at 30 minutes, 2 hour, 12 hour, 24 hour, and 48 hours post-dose
- Frequencies of amount of skin itching and severity of pain at the application site as reported by the subject at 48 hours post-dose
- Frequencies of amount of bruising, erythema, and edema at the application site as assessed by the Investigator at Months 1, 2, 3, 6, 9, 12, and at the 2-week post-study visit
- Proportion of subjects with presence of skin signs and symptoms as assessed by the Investigator at Months 1, 2, 3, 6, 9, 12, and at the 2-week post-study visit

7.1.2 Efficacy Endpoints

- Proportion of subjects with pain freedom at 30 minutes, 2 hours, 12 hours, 24 hours, and 48 hour post-dose
- Proportion of subjects with most bothersome other symptom freedom at 30 minutes, 2 hours, 12 hours, 24 hours, and 48 hours post-dose

- Proportion of subjects with pain relief at 30 minutes, 2 hours, 12 hours, 24 hours and 48 hours post-dose
- Proportion of subjects with nausea freedom at 30 minutes, 2 hours, 12 hours, 24 hours and 48 hours post-dose
- Proportion of subjects with photophobia freedom at 30 minutes, 2 hours, 12 hours, 24 hours and 48 hours post-dose
- Proportion of subjects with phonophobia freedom at 30 minutes, 2 hours, 12 hours, 24 hours and 48 hours post-dose
- Proportions of subjects using rescue medication within 2 hours post-dose
- Proportion of subjects with migraine recurrence at 24 and 48 hours post-dose
- Proportion of subjects with sustained pain freedom from 2 to 24 hours post-dose and from 2 to 48 hours post-dose
- Frequency of responses on the migraine ACT

7.2 Populations for Analysis

The Safety Population will include all subjects who receive any amount of study drug (applied at least one patch). The mITT (modified intent-to-treat) population will include all subjects who receive any amount of study drug to treat a qualifying migraine, and who have efficacy data.

7.3 Statistical Methods

7.3.1 Baseline Characteristics

Demographic and baseline characteristic variables such as age, gender, race/ethnicity, height, and weight will be summarized using descriptive statistics. For categorical variables, frequencies and percentages will be presented. Continuous variables will be summarized using descriptive statistics (n, mean, median, standard deviation [SD], minimum, and maximum).

7.3.2 Safety Analyses

Safety will be assessed by the monitoring and recording of AEs, clinical laboratory tests, vital signs, physical examination findings, ECG parameters, and Investigator and subject reported skin assessments.

All safety analyses will be based on the Safety Population. Adverse events will be coded using the current Medical Dictionary for Regulatory Activities (MedDRA) dictionary (using the latest version) and will be summarized overall and by preferred term and system organ class. Adverse events will also be summarized by severity and relationship to study drug. Serious AEs and AEs leading to discontinuation of study drug will also be summarized.

Actual values and changes from baseline for assessments of clinical laboratory test results, ECG parameters, and vital sign measurements will be summarized at each visit using descriptive statistics (n, mean, SD, median, minimum, and maximum) or shift tables as appropriate. The number and percentage of subjects experiencing Bruising, Erythema, Edema and other skin assessments will also be summarized.

All data gathered will be listed by patient and parameter, separate listings of all abnormal laboratory findings will be provided, and clinically significant abnormalities will be recorded as AEs.

7.3.3 Efficacy Analyses

All efficacy analyses will be based on the mITT Population. The proportion of subjects experiencing pain freedom, most bothersome other symptom freedom, pain relief, nausea freedom, photophobia freedom, phonophobia freedom, those using rescue medication, those with sustained pain freedom, and those with migraine recurrence will be summarized using descriptive statistics. Frequencies and percentages will be provided for all subject responses on the ACT. Further details regarding efficacy analyses can be found in the statistical analysis plan.

8 ADVERSE EVENTS

All systemic and cutaneous AEs, regardless of suspected causal relationship to the investigational products, will be reported as described in the following sections. Subject reported bruising, bleeding, erythema, edema, skin itching and skin pain are collected through the eDiary and will also be recorded as adverse events in the eCRF and followed to resolution.

For all systemic and cutaneous AEs, the investigator must obtain adequate information both to determine the outcome of the AE and to assess whether it meets the criteria for classification as a SAE (see [Section 8.2.1.1](#)) requiring immediate notification (within 24 hours) to the Medical Monitor (MM) and Pharmacovigilance Group (PV) by completing a SAE Report Form. Sufficient information should also be obtained by the investigator to determine the causality of the AE, since he/she is required to assess causality. For systemic and cutaneous AEs with a causal relationship to the investigational product, including **all** application site reactions, investigator is required to follow-up until the event or its sequelae resolve or stabilize at a level acceptable to the investigator.

Pregnancy: In the event that a pregnancy occurs, it will not be considered an AE but requires notification within 24 hours of investigator awareness to the Medical Monitor and Pharmacovigilance Group by completing a Pregnancy Report Form. The investigator will follow the pregnancy and report the outcome. The subject will be discontinued from the study if she becomes pregnant anytime during the study.

8.1 Reporting Period

Collection of systemic and cutaneous AEs will be initiated after the ICF has been signed and will conclude when the post-study procedures are completed (or Early Discontinuation). The investigator will also report to the Medical Monitor and Pharmacovigilance any SAEs that come to his/her attention that occur within 30 days after study drug administration.

8.2 Adverse Event Definitions

8.2.1 Adverse Events (Adverse Experiences)

Collection of systemic and cutaneous AEs will be initiated after the ICF has been signed and conclude when the post-study procedures are completed (or Early Discontinuation). This includes the time between screening and the first patch application.

An AE is any untoward medical event that occurs in a clinical investigation, where a subject is administered a medicinal (investigational) product or medical device, and which does not necessarily have a causal relationship between the event and the treatment. An AE can be any

unfavorable and unintended sign or symptom, including clinically significant abnormal laboratory result, concomitant illness, or worsening of an existing medical condition.

A Treatment Emergent Adverse Event (TEAE) is an event that emerges during treatment having been absent pre-treatment, or worsens relative to the pre-treatment state.

Abnormal laboratory tests that are clinically significant, as determined by the investigator, should be reported as AEs if:

- the test result is associated with accompanying symptoms;
- the test result requires additional diagnostic testing or medical/surgical intervention;
- the test result leads to discontinuation from the study, significant additional concomitant drug treatment, or other therapy;
- the test result is considered to be an AE by the investigator or sponsor.

Merely repeating an abnormal test, in the absence of any of the above conditions, does not constitute an AE. Any abnormal test result that is determined to be an error does not require reporting as an AE.

8.2.1.1 Serious Adverse Event Definitions

A **serious** adverse event (SAE) or reaction is any untoward medical occurrence that at any dose:

- Results in death;
- Is life-threatening (immediate risk of death);
- Requires inpatient hospitalization or prolongation of existing hospitalization (Emergency department outpatient visits for an event not fulfilling any of the other definitions of SAE given do not qualify as hospitalization. If an emergency department visit leads to inpatient hospitalization, it would qualify as an SAE.);
- Results in persistent or significant disability/incapacity; or
- Is a congenital anomaly/birth defect.
- Other important medical events that may not result in death, be life-threatening, or require hospitalization may be considered serious when, based upon appropriate medical judgment, they may jeopardize the patient or subject and may require medical or surgical intervention to prevent one of the outcomes listed in this definition. Examples of such

medical events include allergic bronchospasm requiring intensive treatment in an emergency room or at home, blood dyscrasias or convulsions that do not result in inpatient hospitalization, or the development of drug dependency or drug abuse.

Definition of disability: A substantial disruption of a person's ability to conduct normal life functions.

Life-threatening SAE: Any AE that places the subject, in the view of the investigator, at immediate risk of death from the reaction as it occurred (i.e., it does not include a reaction that had it occurred in a more severe form, might have caused death).

Hospitalization: AEs reported from clinical studies resulting in hospitalization or prolongation of hospitalization are considered serious. Hospitalization does not include the following:

- Rehabilitation facilities;
- Hospice facilities;
- Respite care (e.g., caregiver relief);
- Skilled nursing facilities;
- Nursing homes;
- Routine emergency department admissions; or
- Same day surgeries (as outpatient/same day/ambulatory procedures).

Hospitalization or prolongation of hospitalization in the absence of a precipitating, clinical AE is not in itself an SAE. Examples include:

- Admission for treatment of a preexisting condition not associated with the development of a new AE or with a worsening of the preexisting condition (e.g., for work-up of persistent pre-treatment lab abnormality);
- Social admission (e.g., subject has no place to sleep);
- Administrative admission (e.g., for yearly PE); or
- Pre-planned treatments or surgical procedures that have been noted in the baseline documentation for the entire protocol and/or for the individual subject.

8.2.1.2 Unexpected Adverse Event

An unexpected AE is any AE the nature or severity of which is not consistent with the applicable product information (e.g., current investigator's brochure); or if an investigator's brochure is not required or available, the specificity or severity of which is not consistent with the risk information described in the general investigational plan or elsewhere in the current application, as amended.

8.2.1.3 Severity Ratings

The investigator will evaluate the severity of each AE using the following definitions:

Mild - event may be noticeable to subject; does not influence daily activities; usually does not require intervention.

Moderate - event may be of sufficient severity to make a subject uncomfortable; performance of daily activities may be influenced; intervention may be needed.

Severe - event may cause severe discomfort; usually interferes with daily activities; subject may not be able to continue in the study; treatment or other intervention usually needed.

Life-Threatening – Event that, in the view of the investigator, places the subject at immediate risk of death from the reaction as it occurred (i.e., it does not include a reaction that, had it occurred in a more severe form, might have caused death).

Note the distinction between the severity and the seriousness of an AE. A severe event is not necessarily an SAE. For example, a headache may be severe (interferes significantly with subject's usual function) but would not be classified as serious unless it met one of the criteria for SAEs, listed above. Additionally, an SAE of abdominal pain in an elderly patient that results in hospitalization to rule out diverticulitis may be mild, whereas severe abdominal pain (that interferes with most daily activities) in a younger, stoic patient may not result in hospitalization, and thus be a severe non-serious AE.

8.2.1.4 Relationship to Study Drug

The investigator's assessment of causality must be provided for all systemic and topical AEs (serious and non-serious). An investigator's causality assessment is the determination of whether there exists a reasonable possibility or likelihood that the investigational product caused or contributed to an AE. If the investigator's final determination of causality is unknown and the investigator does not know whether or not the investigational product caused the event, then the event will be handled as "related to investigational product" for reporting purposes. Thus, it is

imperative that all initial SAE reports include an assessment of causality. If the investigator's causality assessment is "unknown but not related to investigational product", this should be clearly documented on study records.

In addition, if the investigator determines an SAE is associated with study procedures, the investigator must record this causal relationship in the source documents and CRF, as appropriate, and report such an assessment in accordance with the SAE reporting requirements, if applicable.

After careful medical consideration, the investigator will evaluate the relationship of each AE to study drug applying the following definitions:

Probably Related

An AE that is likely due to the use of the study drug. The relationship in time is suggestive. An alternative explanation is unlikely, e.g., concomitant drug(s), concurrent illness(es).

Possibly Related

An AE that might be caused by the use of the study drug. The relationship in time is reasonable; therefore, a causal relationship cannot be excluded. An alternative explanation is inconclusive, e.g., concomitant drug(s), concurrent illness(es), but unlikely.

Not Related

An AE that is judged to be clearly due only to extraneous causes (disease or illness, environment, etc.).

The cause must be noted on the appropriate source document and on the AE CRF page.

8.3 Documentation and Reporting of Adverse Events by Investigator

Each AE is to be assessed to determine if it meets the criteria for an SAE. If an SAE occurs, expedited reporting will follow local and international regulations, as appropriate.

All AEs, both expected and unexpected, occurring during this clinical trial must be recorded on the AE page of the eCRF. AEs will be described in precise medical terms, along with the date and time of onset and the date and time of resolution, action taken and outcome. In order to avoid vague, ambiguous or colloquial expressions, the AE should be recorded in standard medical terminology rather than the subject's own words. Whenever possible, the Investigator should group together into a single term signs and symptoms which constitute a single diagnosis. Each AE is to be evaluated for duration, severity, seriousness and causal relationship to the investigational drug. The severity of the AE and its relationship to the test product will be

assessed by the Investigator. When reporting SAEs, the AE form of the eCRF and the SAE form must be completed in a consistent manner. For example, the same AE term should be used on both forms.

8.3.1 Reporting Requirements for Serious Adverse Events

ALL **SERIOUS** ADVERSE EVENTS, REGARDLESS OF CAUSE(S) OR RELATIONSHIP TO STUDY DRUG, MUST BE REPORTED **IMMEDIATELY** TO PHARMACOVIGILANCE GROUP (PV) AND MEDICAL MONITOR (MM) BY TELEPHONE (24/7 Safety Line), FAX, OR EMAIL (Contact info are provided in [Section 8.5](#)).

All SAE reporting will adhere to 21 CFR 312.32 for IND safety reporting, applicable FDA and ICH-GCP regulations.

If an SAE occurs, PV and MM are to be notified within 24 hours of awareness of the event by the investigator. In particular, if the SAE is fatal or life-threatening, notification to PV and MM must be made immediately, irrespective of the extent of available AE information. This timeframe also applies to additional new information (follow-up) on previously forwarded SAE reports. An initial assessment of causality must be included in all SAE reports.

To report an SAE, the investigator must complete the SAE Report Form, and to report a pregnancy, the investigator must complete the Pregnancy Report Form. Occurrence of any SAE/pregnancy must be reported immediately (within 1 working day) once the investigative site has knowledge of the event. The investigator must also provide any relevant information regarding the SAE and respond to requests for follow-up in a timely manner. All SAEs will also be reported on the AE CRF page and concomitant medications administered in association with the SAE will be documented on the appropriate CRF.

If an SAE occurs and comes to the attention of the investigator after study termination within 30 days of the last dose of study drug(s), it must be reported immediately to the sponsor in the same way as the SAEs occurring during the study.

8.3.1.1 Investigator Reporting Responsibilities to the Independent Ethics Committee and Other Agencies

The investigator must promptly report to the IRB/IEC or independent ethics committees (IEC) all changes in the research activity and all unanticipated problems involving risk to human subjects or others. This includes all SAEs that have occurred at the study site and all study-related SAEs that have resulted in an expedited safety report to the FDA (serious, unexpected SAEs possibly or probably related to study drug). The investigator must send all IRB/IEC documentation (including notifications and acknowledgements) to the sponsor or its

designee. The investigator must not make any changes in the research without IRB/IEC approval, except where necessary to eliminate apparent immediate hazards to human subjects.

8.3.2 Reporting Requirements for Non-Serious Adverse Event

Non-serious systemic and skin AEs experienced after the randomization phase of the study will be reported on the AE CRF pages, which will be submitted to the sponsor or its designee.

8.4 Follow up of Adverse Events

All SAEs must be followed up until resolution or, in the investigator's opinion, a stable condition is reached, or until the subject is lost to follow up. All follow up reports should be made by completing the SAE Report Form and by utilizing the same reporting procedures as the initial report.

Based on the medical judgment of the investigator, all non-serious systemic and skin AEs will be followed until 14 days after the final two week safety follow-up visit. All non-resolved, non-serious systemic and skin AEs beyond such date will be recorded as "ongoing" without further follow up.

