3.2.6 Early Termination

3.2.6.1 Withdrawal of Subjects

Subjects may be withdrawn from treatment or from the study for the following reasons:

- Subject did not experience at least 6 qualifying migraines within 12 weeks after patch and applicator dispensation (Visit 3);
- At their own request or at the request of their legally authorized representative;
- If, in the investigator's opinion, continuation of treatment would be detrimental to the subject's well-being;
- If the subject experiences any AE believed to be possibly or probably related to study drug and severe enough to warrant withdrawal of treatment;
- If the subject starts and continues to use a prohibited drug, as listed in [Section 6.2.11](#);
- If the subject is non-compliant with the study drug, eDiary completion, or any other requirement of this protocol; or
- If a subject becomes pregnant anytime during the study.

Subjects who early terminate from the study after applying study medication, will return for an early termination visit and a two-week safety follow-up visit if they applied any patches. For all subjects who are withdrawn from study drug or from the study, the reason must be recorded on the appropriate source document and on the appropriate CRF. The subject must be followed up to establish whether the reason was an AE, and, if so, this must be reported in accordance with the procedures in [Section 8.3](#). Subjects with ongoing systemic and skin AEs at study termination will be followed until all significant changes have resolved or become medically stable.

To the extent possible, all examinations scheduled and all data normally collected at completion of the study (the final study visit) must be performed on all subjects who receive study drug but do not complete the study according to protocol. These assessments must be done at the time of the subject's early termination visit.

The investigator must make at least three documented attempts (phone, email, etc.) to contact subjects lost to follow-up until the time of database lock. This includes one certified letter sent to the subject's primary place of residence. A copy must be maintained in the source documentation.

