6.1.8 Two Week Post Study Safety Visit (Visit 10)

This visit will occur 14-28 days after the End of Study Final Visit (or Early Termination visit). The following procedures will be performed:

- Record vital signs: temperature, respiratory rate (RR), blood pressure (BP), and heart rate (HR)
- Perform Investigator Skin Assessment (presence of blisters, scaly or flakey skin, erosions or open sores, scarring, hyperpigmentation, bruising, redness, and/or swelling) of upper arm(s) where patches have been applied
- Any cutaneous signs or symptoms found on the investigator skin assessment will be recorded as an adverse event on the eCRF and followed to resolution.
- Record concomitant medications

Record adverse events

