6.2.13 Subject Reported and Investigator Reported Skin Assessments

Subject reported bruising, bleeding (at 30 minutes only), erythema, edema, skin itching and skin pain are collected through the eDiary and will also be recorded as adverse events in the eCRF. The subject is also provided a Subject Skin Grading Card to help him/her assess whether they have any skin reaction(s) and how to grade any reaction(s) (see [Appendix 4](#)). If the subject contacts the investigator at any time point for worsening or non-resolving reactions, the subject must be seen for an unscheduled visit. The skin reaction(s)/symptom(s) will be assessed, recorded as adverse events in the eCRF and followed to resolution.

In addition, investigator skin assessments in [Section 6.2.13.1](#) will be completed at each in-clinic visit during the treatment period. Any findings related to the upper arm(s) where the patches were applied will be recorded as an adverse event in the eCRF and followed until the signs/symptoms resolve.

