APPENDIX 6 – Investigator Assessment Rating for Bruising, Erythema, Edema and

The Bruising, Erythema, and Edema assessment will be performed by the investigator at each in clinic visit starting at Month 1 and performed using the following ratings. When determining the percentage of application sites affected for a given sign, the investigator should consider the entire outer arm from the top of the shoulder to the elbow as the denominator. Any findings with ratings of 1 (mild), 2 (moderate), or 3 (severe) must be recorded as an adverse event in the eCRF and followed to resolution. The investigator will use the definitions of AE Severity Ratings for Mild, Moderate, Severe, Life-Threatening ([Section 8.2.1.3](#)) to assess the Severity of the AE.

Symptom	Rating (circle)
M207 application sites have bruising spots?	0 (clear) = None 1 (mild) = $\leq 25\%$ Present in the upper arm region of all M207 applications 2 (moderate) = ≥ 26 to $\leq 50\%$ Present in the upper arm region of all M207 applications 3 (severe) = $> 50\%$ Present in the upper arm region of all M207 applications

Symptom	Rating (circle)
Skin Erythema	0 (clear) = None 1 (mild) = $\leq 25\%$ Present in the upper arm region of all M207 applications 2 (moderate) = ≥ 26 to $\leq 50\%$ Present in the upper arm region of all M207 applications 3 (severe) = $> 50\%$ Present in the upper arm region of all M207 applications

Symptom	Rating (circle)
Skin Edema	0 (clear) = None 1 (mild) = $\leq 25\%$ Present in the upper arm region of all M207 applications 2 (moderate) = ≥ 26 to $\leq 50\%$ Present in the upper arm region of all M207 applications 3 (severe) = $> 50\%$ Present in the upper arm region of all M207 applications

The photographs below for bruising, erythema, and edema are examples for the investigator as to what these skin reaction(s) in the upper arm region may look like. The investigator will use the definitions of AE Severity Ratings for Mild, Moderate, Severe, Life-Threatening ([Section 8.2.1.3](#)) to assess the Severity of the AE.

[figure not shown]
Bruising

None (Clear)

Mild

Moderate

Severe

Erythema

[figure not shown]
None (Clear)

Mild

Moderate

Severe

Edema

[figure not shown]
None (Clear)

Mild

Moderate

Severe

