14.3.1.3a	Study Drug-Related Treatment Emergent Adverse Events by System Organ Class and Preferred Term - ALL Adverse Events Safety Set
14.3.1.3b	Study Drug-Related Treatment Emergent Adverse Events by System Organ Class and Preferred Term - E-Diary Skin Assessment Reported Adverse Events Safety Set
14.3.1.3c	Study Drug-Related Treatment Emergent Adverse Events by System Organ Class and Preferred Term - Other Subject Reported Adverse Events Safety Set
14.3.1.4	Serious Treatment Emergent Adverse Events by System Organ Class and Preferred Term-ALL Adverse Events Safety Set
14.3.1.5	Treatment Emergent Adverse Events of Special Interest by System Organ Class and Preferred Term- ALL Adverse Events Safety Set
14.3.1.6a	Treatment Emergent Adverse Events by Maximum Severity by System Organ Class and Preferred Term - ALL Adverse Events Safety Population
14.3.1.6b	Treatment Emergent Adverse Events by Maximum Severity by System Organ Class and Preferred Term - E-Diary Skin Assessment Reported Adverse Events Safety Population
14.3.1.6c	Treatment Emergent Adverse Events by Maximum Severity by System Organ Class and Preferred Term - Other Subject Reported Adverse Events Safety Population
14.3.2.1	Summary of Subject Reported Skin Assessment by Time After Patch Application Safety Population
14.3.2.2	Summary of Subject Reported Skin Assessment by Time After Patch Application - All Migraines Safety Population
14.3.2.3	Summary of Investigator Reported Skin Assessment by Visit Safety Population
14.3.2.4	Number of Treated Qualifying Migraines per Subject Safety Population
14.3.2.5	Number of Treated Qualifying Migraines per Month by Subject Safety Population
14.3.2.6	Number of Symptoms by Time Points - All Migraines Safety Population
14.3.3.1.1	Shift in Laboratory Tests: Hematology Safety Population
14.3.3.2.1	Shift in Laboratory Tests: Serum Chemistry Safety Population

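### Section 8.4 ends follow-up of non-serious skin AEs on a fixed date, while Section 8 and the skin-assessment sections require unresolved application site reactions to be followed further

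*Protocol*

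**What the plan says.** Protocol Section 8.4 covers non-serious AEs, naming skin AEs along with systemic ones. Subject to the investigator's medical judgment, they "will be followed until 14 days after the final two week safety follow-up visit". Anything unresolved after that is entered as ongoing, with no further follow-up.

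Other parts of the protocol set no time limit and do not refer to 8.4:

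- **Section 8**, for related AEs and expressly for all application site reactions: "investigator is required to follow-up until the event or its sequelae resolve or stabilize at a level acceptable to the investigator". The same section says that subject-reported skin reactions are followed to resolution.
- **Section 6.1.8**, for signs or symptoms at Visit 10: "found on the investigator skin assessment will be recorded as an adverse event on the eCRF and followed to resolution".
- **Section 6.2.13**, for investigator findings on the upper arm: "will be recorded as an adverse event in the eCRF and followed until the signs/symptoms resolve".
- **Appendix 6**, for bruising, erythema or edema rated 1 to 3: "must be recorded as an adverse event in the eCRF and followed to resolution". Appendix 5 gives the same end point for blisters, scaling, erosions, scarring and pigment change.
- **Section 3.2.6.1**, for AEs ongoing when a subject terminates: subjects "will be followed until all significant changes have resolved or become medically stable".

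SAP Section 11.2 plans an average time to resolution for skin AEs reported in the eDiary. It gives no rule for events still ongoing, and SAP Section 6.3 says that missing data are not imputed unless otherwise specified.

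**The concern.** The primary objective is long-term safety under repeated use, and skin reactions at the patch site are a central part of it. A site that applies 8.4 may close a reaction that Section 8 obliges it to keep following. A site that applies Section 8 or Section 6 would continue. The same reaction could then be handled in two ways, and a monitor could not say which is the deviation. In the data, events marked ongoing would mix reactions that truly persisted with reactions that nobody followed.

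There is a second fault on the other side. Follow-up to resolution has no end point for a permanent mark. Only Sections 8 and 3.2.6.1 allow follow-up to stop once the condition is stable. The protocol therefore lacks one workable rule.

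**Working it through.** **1. Where the rules collide.** Consider a non-serious application site reaction on the day 8.4 closes it.

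| State at the 8.4 cut-off | Section 8 (resolve or stabilise) | 6.1.8, 6.2.13, Appendices 5 and 6 (resolve) |
|---|---|---|
| Resolved | no conflict | no conflict |
| Stable, not resolved | no conflict under the rule for related AEs | conflict |
| Neither resolved nor stable | conflict | conflict |

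**2. How much follow-up 8.4 allows.** Visit 10 is 14 to 28 days after the final or early termination visit (Section 6.1.8). The early termination visit is 7 to 14 days after the last patch (Section 6.1.6). Section 8.4 adds 14 days after Visit 10.

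- First seen at Visit 10: 14 days.
- First seen at the final visit: 14 + 14 = 28 to 28 + 14 = 42 days.
- Early terminator, counted from the last patch: 7 + 14 + 14 = 35 to 14 + 28 + 14 = 56 days.

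**3. What share could be unresolved.** The documents give no durations, so this is an illustration only. Assume that the remaining duration is exponential with mean m. The share unresolved after W days is exp(−W/m).

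| Assumed m (days) | W = 14 | W = 28 to 42 | W = 35 to 56 |
|---|---|---|---|
| 7 | 13.5% | 1.8% to 0.2% | 0.7% to 0.03% |
| 14 | 36.8% | 13.5% to 5.0% | 8.2% to 1.8% |
| 30 | 62.7% | 39.3% to 24.7% | 31.1% to 15.5% |
| 90 | 85.6% | 73.3% to 62.7% | 67.8% to 53.7% |

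These are shares of reactions that start or are first seen at the very end of a subject's participation, not of all reactions. They count unresolved reactions whether stable or not, so they overstate the conflict with Section 8.

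**4. The SAP average.** A time to resolution needs an end date, and an ongoing event has none. With no imputation and no censoring rule, I infer that the average would cover resolved events only. To size this for completers, assume onsets spread evenly over the 336 days to Month 12, exponential durations with mean m, and follow-up for a further t = 28 or 42 days.

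- Share ongoing = (m/336) × [exp(−t/m) − exp(−(336 + t)/m)].
- Mean of resolved events = m − E[c·exp(−c/m)] / (1 − share ongoing), where c is the follow-up available to each event, uniform from t to 336 + t.

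| Assumed m (days) | Ongoing, t = 28 / 42 | Resolved-only mean, t = 28 / 42 |
|---|---|---|
| 7 | 0.04% / 0.005% | 6.99 / 7.00 |
| 30 | 3.5% / 2.2% | 27.9 / 28.4 |
| 90 | 19.2% / 16.4% | 64.0 / 65.7 |

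The effect is negligible for reactions lasting days and material only if they typically last months.

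**The case against.** The strongest reply is that the conflict is narrow and the plan already covers what matters most.

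- **Stability.** Section 8 lets follow-up end once a reaction is stable at a level the investigator accepts. A mark that is stable at the cut-off meets both 8.4 and the Section 8 rule. This stands. A reader might infer that any Visit 10 reaction lasting more than 14 days breaches Section 8, and the text does not support that.
- **Early termination.** A reader might also count Section 3.2.6.1 as a general contradiction. It sits under withdrawal of subjects and concerns significant changes only, so it lends little support for minor reactions in completers.
- **The 14-day window.** Unused patches are collected and the arm is inspected at the final visit (Section 6.1.6). A reaction first recorded at Visit 10 has therefore appeared late or been missed. The 14-day column above is a corner case, and its 14% to 86% should not be read as the share of reactions that lose follow-up.
- **Existing safeguards.** Site reactions needing further evaluation or care, "as well as those resulting in scarring are considered adverse events of special interest", with photographs sent to the sponsor within 24 hours of the clinic visit. The SAP index lists a table of "Treatment Emergent Adverse Events of Special Interest by System Organ Class and Preferred Term". SAP Section 11.2.2 tabulates skin findings by visit through Visit 10. SAEs are followed until resolved or stable under 8.4 itself. These safeguards limit the harm. They do not settle the final outcome of a reaction after Visit 10, and pigment change that needs no care falls outside the special-interest definition.
- **Investigator judgment.** The opening phrase of 8.4 could be read as leaving room to continue. It does not reconcile the texts, because 8.4 closes unresolved events at a fixed date while Section 8 makes continued follow-up an obligation.
- **The SAP average.** Exclusion of ongoing events is inferred, not stated. The summary covers eDiary reactions only, not investigator-found scarring or pigment change. It is not among the listed endpoints and has no titled table. A reader might infer a materially biased duration estimate, but the documents do not show one.

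**Conclusion.** The inconsistency is real, and nothing in the documents resolves it. Section 8.4 contradicts Section 8 for application site reactions that are neither resolved nor stable at the cut-off. It contradicts Sections 6.1.8 and 6.2.13 and Appendices 5 and 6 for any reaction not yet resolved.

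The follow-up windows come directly from the visit schedule. The number of reactions affected is unknown, because no durations are given. It is probably small: only reactions open at the end of a subject's participation are exposed, and Section 1.2.2.4 describes dermal events in the earlier study as mostly mild and short-lived. That evidence is from single use, so it does not settle the matter for repeated use.

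No sample size, power or error rate is involved. Severity is low. The SAP point is a minor, optional addition.

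**What to change.** Amend Section 8.4 so that application site reactions and other AEs related to study drug are followed until they resolve or stabilise at a level acceptable to the investigator, as Section 8 already requires. Keep the limit of 14 days after Visit 10 only for non-serious AEs judged not related.

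Use the same resolve-or-stabilise wording wherever the protocol now says to resolution: Section 8 for subject-reported reactions, Sections 6.1.4 to 6.1.6, 6.1.8 and 6.2.13, and Appendices 5 and 6. This gives a permanent mark a defined end point. A stable pigment change would still be closed unresolved, but under one rule at every site.

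Optional in SAP Section 11.2: label the average time to resolution as covering resolved events only, and report beside it the number and percentage of events unresolved at last contact.

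The cost is a protocol amendment with IRB/IEC approval and slightly longer follow-up of a few subjects. The SAP addition is one sentence and one count, using the resolution dates and outcomes that Section 8.3 already collects.
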